6.6. Risk-Benefit Ratio

Given the limited risk associated with participation in surveys, we anticipate that the benefits of this study will far outweigh the risks involved.

7. Analysis

7.1. Primary Endpoint

The primary endpoint is completion of LCS counseling, defined by completion of a telemedicine visit, in person counseling visit (CPT G0296), or documentation of LCS counseling in EHR provider notes. Secondary endpoints include completion of LDCT for LCS, reach (defined as proportion of patients who engage with the direct outcome divided by those who are invited to engage with the outreach), and referral or completion of tobacco cessation treatment.

7.2. Sample Size and Statistical Power Calculations

With a sample size of 600 patients across the two arms, the study be powered (1- β =80%, Two-sided α =0.05) to detect a minimum difference of 5.9- 11.4% in the primary outcome (LCS counseling) between the study arms, depending on completion rate (10-90%) of in controls.

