Recommendations for annual lung cancer screening (LCS) are largely based on the results of the National Lung Screening Trial (NLST) that found a 20% reduction in lung-cancer specific mortality with annual low-dose computed tomography (LDCT) in comparison to chest radiography (1-2). In addition to potential benefits, substantial harms are linked to LCS including high rates of false positives, radiation exposure, and surgical complications (3). Based on this evidence, in 2013, the United States Preventive Services Task Force (USPSTF) provided a Grade "B" recommendation for annual LCS for asymptomatic adults aged 55-80 who are or have been heavy smokers (≥30 pack-years of smoking and quit-date < 15 years ago), and are able to undergo surgery (4). In 2015, The Centers for Medicare and Medicaid Services (CMS) issued national coverage for LCS requiring that LCS counseling, which must include shared decision-making and tobacco cessation counseling, occur prior to LCS (5). CMS also provides reimbursement for LCS counseling to further support providers to engage in meaningful, collaborative conversations about LCS with patients (6, 7). Despite widespread support, uptake and implementation of LCS across the United States has been low (estimated 3-5% screening-eligible population screened) (8). Locally, since the onset of the Penn Medicine LCS Program in 2014, over 3,500 individual patients have received LCS; however, documentation and reimbursement of LCS counseling (under CPT G0297) is very low.

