2.1. Specific Aims

The specific aims of this single-center pilot randomized trial are:

- 1. Pilot test the effect and feasibility of using direct outreach and telemedicine referral to increase LCS counseling and LCS uptake among screening-eligible patients.
- 2. Explore the moderating effects of individual and cognitive moderators (patient characteristics, risk factors, and psychological beliefs) on screening intention and uptake.

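### Does the stated detectable difference of 5.9–11.4 points overstate what 600 patients can detect when few controls complete counseling?

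*Combined protocol and SAP*

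**What the plan says.** The combined protocol and SAP states its power in one sentence, in section 7.2. The inputs are "With a sample size of 600 patients across the two arms" and "1- β =80%, Two-sided α =0.05". The result is the ability to "detect a minimum difference of 5.9- 11.4% in the primary outcome (LCS counseling) between the study arms, depending on completion rate (10-90"%) among controls. The sentence does not say which control rate gives which difference, whether the difference is a rise or a fall, or what control rate is expected.

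Three other places bear on it. Section 3.3 (Schema) sets 1:1 randomization, hence 300 per arm. Section 2.1 (Specific Aims) gives the direction sought: "telemedicine referral to increase LCS counseling and LCS uptake among screening-eligible patients". Section 1 (Background and Rationale) describes current practice: national uptake of screening is low ("estimated 3-5% screening-eligible population screened"), and at the trial's own health system "documentation and reimbursement of LCS counseling (under CPT G0297) is very low".

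**The concern.** Two ranges printed in ascending order in one sentence invite the reader to match their ends: 5.9 points with a 10% control rate. The background makes the low end look like the relevant one, since it describes both screening and documented counseling as rare. For the increase the trial seeks, that match is false. Within 10–90%, an increase of 5.9 points is detectable with 80% power only if 90% of controls already complete counseling, which nothing in the documents suggests. From 10%, 5.9 points is detectable only as a fall.

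If the plan did claim 80% power for 5.9 points at a 10% control rate, the trial would be weaker than advertised, and a null result might be taken to exclude a gain of about 6 points when it could not.

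**Working it through.** **Inputs.** n = 300 per arm (600 in section 7.2, 1:1 in section 3.3); two-sided α = 0.05, so z = 1.96; power 80%, so z = 0.84; control rates 10–90% (section 7.2); direction an increase (section 2.1). Section 7.2 states no dropout allowance, and none is applied.

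**Formula.** For control rate p₁, intervention rate p₂ = p₁ + d and mean rate p̄ = (p₁ + p₂)/2:

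- SE₀ = √[2p̄(1 − p̄)/n]
- SE₁ = √[p₁(1 − p₁)/n + p₂(1 − p₂)/n]
- power = Φ[(d − 1.96·SE₀)/SE₁]

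The minimum detectable increase is the d that makes power 80%.

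**Step 1: reproduce the stated range.** Solving for d at n = 300:

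| Control rate | Detectable increase (points) |
|---|---|
| 10% | 7.91 |
| 20% | 9.88 |
| 30% | 10.92 |
| 40% | 11.37 |
| 45% | 11.41 |
| 50% | 11.34 |
| 60% | 10.86 |
| 70% | 9.89 |
| 80% | 8.33 |
| 90% | 5.85 |

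The smallest value is 5.85, which rounds to 5.9. The largest is 11.41, which rounds to 11.4. These are the two printed figures.

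Check at the lower end, 90% against 95.9%: SE₀ = 0.0209, SE₁ = 0.0208, (0.059 − 1.96 × 0.0209)/0.0208 = 0.87, power 80.7%. Check at the upper end, 45% against 56.4%: SE₀ = 0.0408, SE₁ = 0.0406, (0.114 − 1.96 × 0.0408)/0.0406 = 0.84, power 79.9%.

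**Step 2: test the pairing by order.** If 5.9 went with 10%, then 11.4 would go with 90%. For an increase that means 90 + 11.4 = 101.4%, which is impossible. The sentence can only mean a minimum and a maximum over the range, as in Step 1.

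**Step 3: the 10% control rate.** The detectable increase is 7.91 points (7.87 with unpooled variance, 7.84 by arcsine, 8.29 with continuity correction). For 10% against 15.9%: SE₀ = 0.0274, SE₁ = 0.0273, (0.059 − 1.96 × 0.0274)/0.0273 = 0.19, power 58%. Reaching 80% there would take 508 per arm. These figures are right, but 7.91 lies inside 5.9–11.4, so they contradict nothing in section 7.2.

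**Step 4: the low rates in the background.** The same formula below 10%:

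| Control rate | Detectable increase (points) | Power for 5.9 points |
|---|---|---|
| 3% | 5.26 | 87% |
| 4% | 5.78 | 81% |
| 5% | 6.23 | 76% |

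If controls completed counseling at the 3–5% that section 1 gives for screening, the trial's sensitivity would be close to the best figure printed, or slightly better.

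**The case for a change.** The strongest case for the concern is that the sentence, though correct, is of little use. It gives no direction and no planning rate, and its most favorable figure comes from a control rate that the background makes implausible. At control rates of 10–30% the detectable increase is 7.9 to 10.9 points, and power for 5.9 points is 58% at 10% and 40% at 20%. No two-sided variant tried brings the detectable increase at 10% down to 5.9; the lowest, 6.86, uses the control-rate variance for both arms and does not reproduce the stated range. Section 1 also says the results are meant to support a larger grant application, so a clear sensitivity statement would help.

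The numbers stand, and so does the point about clarity: section 7.2 could attach each difference to its control rate and name an expected rate. That is missing detail, not a wrong figure.

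The background does not supply the missing rate. The 3–5% is national uptake of the scan, and the local remark concerns documentation and reimbursement under a billing code. The primary outcome (section 2.2) is wider and counts counseling documented in provider notes. Controls are consenting patients who receive decision-aid information and program contact details and are encouraged to raise screening with their providers (section 5.7). Their completion rate is unknown, and a pilot may reasonably show a wide range. Dropping the 90% case would be a matter of preference.

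The feared misreading of a null result is also weak. Such a result would be judged by its estimate and confidence interval, and the printed range itself warns that the detectable difference may be as large as 11.4 points.

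**Conclusion.** The concern does not hold. Both ends of the stated range reproduce for an increase with 300 per arm (5.85 and 11.41 points), and section 7.2 makes no claim of 80% power for 5.9 points at a 10% control rate. The 7.9 points and 58% power at that rate are correct and consistent with the plan. At control rates of 3–5% the detectable increase is 5.3 to 6.2 points, so low control rates as such do not undercut the stated sensitivity.

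This rests on 1:1 allocation of 600 patients, a two-sided 0.05 pooled two-proportion test as a stand-in for the planned logistic regression, outcome data on everyone enrolled, and reading the sentence as a minimum and maximum. That reading is the only one that is arithmetically possible for an increase. Linking each difference to a control rate would be an optional improvement in wording.

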7.3. Statistical Methods

Primary Analysis:

Intention-to-treat (ITT) analyses using logistic regression to assess the overall effect of the intervention on completion of LCS counseling among those who enroll.

Secondary Analysis:

Baseline survey and clinical data will be used to explore potential predictors (demographics, cognitive biases, and other factors) on screening intention and LDCT uptake. We will also explore potential differences by patient groups based on age, race, and sex. We will fit multivariable regression models with intervention, moderator, and interaction terms to assess effect modification based on significance of the interaction term. These analyses are exploratory.

8. Study Monitoring and Safety

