Challenges of implementing LCS include substantial barriers to identifying screening-eligible patients, supporting high-quality decision-making, and remaining uncertainties regarding risks and benefits (9,10). For other types of cancer screening, insights from behavioral economics have been applied to understand how cognitive biases impact screening uptake (11-13). Yet for LCS, there is limited to no evidence on how these biases effect screening behaviors (14). Given the complexities of LCS, in which the benefits do not clearly outweigh the harms, understanding how these biases impact screening can help inform development of intervention strategies that both support informed decision-making and increase uptake among eligible patients. Leveraging the Penn LCS Program, and existing LCS database developed within our Penn Population Center of Excellence in Precision Lung Cancer Screening Project, we will combine insights from behavioral economics and connected health strategies to pilot test connected health approaches including telemedicine visits to improve frequency and quality of LCS counseling, and to explore cognitive moderators of LCS screening intention and uptake.

Results from this study will be used to develop tailored outreach and identify effective strategies for expanding our pilot study. We will seek R01-level funding to assess how proposed strategies and outreach impacts screening uptake across diverse populations. The long-term goal is to decrease lung cancer burden by increasing utilization of LCS and providing clinicians and patients with effective strategies to deliver high-quality, patient-centered care. This study will also advance scientific understanding of the mechanisms that drive or hinder health behavior in the context of cancer prevention.

2. Objectives

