3.4. Accrual and Duration

To ensure our study is aligned with workflows of the Penn LCS Program, we will invite potentially eligible adults in randomly sampled, sequential batches (approximately four batches of 1,500 each for a total of 6,000 invited patients). Based on previous pragmatic trials (15), we anticipate that approximately 20% of these patients will respond to the invitation. Of these estimated 1,200 adults, we anticipate that 50% will meet screening criteria and will enroll into the study, resulting in an estimated sample size of 600. After each batch, we will assess and adapt as needed to reach the sample size and to align with clinical capacity.

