4.2. Assignment

Participants will be randomized individually to 1 of the 2 arms using REDCap randomization module (1:1 stratified by study batch). Patients will be randomized at the point of survey invitation due to the structure of REDCap randomization module and the study design.

5. Study Procedures

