5.5. Allocation

Participants will be randomized in the REDCap platform to one of the two study arms, as described in §4.1. Patients are considered assigned to the Intention-to-Treat analyses upon confirmation of eligibility and enrollment in the study.

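### Randomization is stratified by study batch but the primary logistic regression has no batch term: a minor, nearly free improvement, not an error

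*Combined protocol and SAP*

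**What the plan says.** - **Randomization (4.2).** Allocation is individual and "1:1 stratified by study batch". Sections 3.4 and 5.2 describe about four batches of 1,500 invitations, each drawn at random from the potentially eligible pool and sent one after another. Section 3.4 adds: "After each batch, we will assess and adapt as needed to reach the sample size and to align with clinical capacity".
- **Primary analysis (7.3).** "Intention-to-treat (ITT) analyses using logistic regression to assess the overall effect of the intervention on completion of LCS counseling among those who enroll". The Protocol Summary says the same in substance. Neither place names batch, an odds ratio, a risk difference or a confidence interval. Model terms are listed only for the exploratory moderator analyses, and batch is not among them.
- **Analysis set (5.5).** "Patients are considered assigned to the Intention-to-Treat analyses upon confirmation of eligibility and enrollment in the study".
- **Sizing (7.2).** 600 patients, 80% power and two-sided 0.05 give a detectable difference of 5.9 to 11.4% "in the primary outcome (LCS counseling) between the study arms", "depending on completion rate (10-90%) of in controls".

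**The concern.** An analysis normally carries the factors on which randomization was stratified. If batches differ in counseling rate and the arms are balanced within batch, an arm-only model leaves between-batch variation in its standard error although the design has already removed it from the comparison. The test is then a little conservative and some precision is lost. The wording in 7.3 also allows a model with or without batch, and the two give slightly different odds ratios, so the choice could be made after data are seen. What is at stake is a small amount of power and a clear pre-specification, not the validity of the result.

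**Working it through.** **1. The plan's own figure.** Inputs from 7.2: 300 per arm, two-sided 0.05 (z = 1.960), 80% power (z = 0.842). Solve for d, with pt = pc + d and p̄ the mean of pc and pt:

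d = 1.960·√[2p̄(1−p̄)/300] + 0.842·√[(pc(1−pc) + pt(1−pt))/300]

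| Control rate | Detectable increase | Odds ratio |
|---|---|---|
| 10% | 7.91 points | 1.96 |
| 45% | 11.41 | 1.58 |
| 50% | 11.34 | 1.59 |
| 90% | 5.85 | 2.57 |

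The smallest and largest values match 5.9 and 11.4. The trial was sized on an absolute difference with a two-proportion test.

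**2. What the arm-only model already gives.** With arm as its only term, the logistic model is saturated: its fitted probabilities are the two observed proportions. An odds ratio of 1.587 with 50% observed in controls gives 1.587/(1 + 1.587) = 61.3%, that is +11.3 points. The risk difference therefore follows directly, and the test is asymptotically the one used in 7.2.

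**3. Batch differences (assumed; the documents give none).** Take four equal batches with equally spaced log-odds and SD s. The spacing is s/√1.25, so the highest-versus-lowest batch odds ratio is exp(3s/√1.25): 2.2 at s = 0.3 and 5.0 at s = 0.6.

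**4. Hand check at control 50%.** At s = 0.6 the batch rates are 30.9, 43.3, 56.7 and 69.1%. Their variance is (0.191² + 0.067²)/2 = 0.0205, or 0.0205/0.25 = 8.2% of the total. Removing it multiplies the standard error by √(1 − 0.082) = 0.958.
- Exact balance within batch: the arm-only test in effect uses 1.960/0.958 = 2.045, so null rejection is about 4.1%.
- Chance balance: the arm-only standard error is right. Adding batch raises power from 80% to Φ(2.802/0.958 − 1.960) = 83.2%.

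At s = 0.3 the share is 2.2% and the factor 0.989. These give about 4.7% and 80.9%.

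**5. Simulation.** 40,000 runs per setting, n = 600, Wald tests, overall rates held at the sized values. Monte Carlo SE is about 0.2 points for power and 0.11 for null rejection. Power in %, arm-only / with batch, equal batches:

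| Balance within batch | Control | SD 0 | SD 0.3 | SD 0.6 |
|---|---|---|---|---|
| Exact | 10% | 80.1/80.2 | 80.5/80.8 | 80.9/82.0 |
| Exact | 50% | 80.7/80.8 | 80.4/80.6 | 81.7/83.4 |
| Exact | 90% | 80.6/80.7 | 80.6/80.8 | 80.9/81.6 |
| Chance | 50% | 79.7/79.7 | 80.1/80.6 | 79.8/82.8 |

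Over all settings, including batches of 240/180/120/60, the change in power (taken before rounding) was:
- Exact balance: about +0.1 points at SD 0 to 0.15, +0.1 to +0.4 at 0.3, and +0.5 to +1.6 at 0.6.
- Chance balance: −0.1 to +0.3, 0 to +0.8, and +0.5 to +3.2.

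Null rejection was 3.6 to 4.9% arm-only and 4.6 to 5.4% with batch under exact balance. Under chance balance it was 4.6 to 5.2% for both models. Coverage of the standardized risk-difference interval was 94.5 to 95.2%. Its half-width at control 50% was 7.9 points arm-only, and 7.8 (SD 0.3) or 7.5 (SD 0.6) with batch.

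**6. Side effects of adding batch.** For the same +11.3 points at control 50%, the odds ratio is 1.59 unadjusted, 1.60 with batch at SD 0.3 and 1.65 at SD 0.6. A batch with no events or all events makes its batch term inestimable. In the most extreme setting (240/180/120/60, control 90%, SD 0.6) this happened in about 13% of null trials and 25% under the sized effect. At SD 0 to 0.15 it was 0 to 4%.

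**The case against.** The best reply is that batches are random samples of one eligible pool, and that 3.4 allows adaptation only to reach the sample size and fit clinical capacity. Nothing in the documents supports a between-batch odds ratio of 5. With small batch differences the gain is near the simulation error, and this is a single-center pilot. All of that stands as to size. It does not remove the point: batches run in sequence over most of 2021 (3.5), so conditions may shift, and following the randomization costs almost nothing.

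Three stronger readings are tempting, and the documents do not support them.

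- **Ignoring the stratification makes the primary test invalid.** It does not. Arm-only null rejection stayed at or near 5%, or below it.
- **The arm-only test is generally conservative.** That needs exact balance among enrolled patients within batch. Section 4.2 says "Patients will be randomized at the point of survey invitation", whereas 5.5 fixes the analysis set later, at confirmed eligibility and enrollment. Balance among enrollees may then hold only by chance, and both tests reject at close to 5%. Sections 3.3 and 5.7 place randomization later, and no block size is given, so the documents do not settle which case applies.
- **An odds ratio cannot be set against the sized difference because the control rate is open from 10 to 90%.** That range is uncertainty at the design stage. At analysis the control rate is observed, and step 2 shows that the difference follows directly. Naming the risk difference is a reporting convenience.

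**Conclusion.** This is a minor free improvement. The primary model in 7.3 omits the one factor on which randomization is stratified; the planned test is nevertheless valid and the 7.2 figures are correct. Adding batch is worth about nothing if batches do not differ, about 0 to +1 point of power at SD 0.3, and about +0.5 to +3 points at SD 0.6. These SDs are assumptions, and the larger one is generous for randomly sampled batches. The main benefit is an analysis that matches the randomization and is fixed in advance.

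**What to change.** In 7.3, with the Protocol Summary brought into line, state:

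> The primary model is a logistic regression of LCS counseling on arm and batch, including every ITT patient (5.5); the test is that of the arm term. A batch with no events or all events is pooled with the adjacent batch. The standardized (marginal) risk difference with 95% CI is reported alongside the odds ratio.

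Naming the arm term as the test matters because the test and the risk-difference interval can occasionally disagree (about 1% of simulated trials at control 90% under the sized effect).

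The cost is a few lines of text and code, with no new data and no change to the 600 patients. The downside is negligible: the odds ratio becomes conditional on batch and slightly larger than the unadjusted one, and the risk difference beside it keeps the result on the scale of 7.2.

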Interventions	 Following enrollment, all patients will be asked to complete a brief baseline survey assessing demographics, smokingand LCS cancer beliefs, and screening intention using measures previously applied in other studies, and will receive \$20 upon completion. Following completion of the baseline survey, patients will be randomized into one of the two treatment arms. All patients will receive brief information on lung cancer screening risks and benefits adapted from validated decision support tool. Following survey completion: a) Patients in the usual care arm will be provided with contact information for the Penn LCS Program and encouraged to discuss LCS with their providers and b) Patients in the intervention arm will be offered to be directly referred to the LCS telemedicine program and asked for their permission to provide their phone number to the Penn LCS navigator. All patients will be re-contacted approximately 6-8 weeks after enrollment to conduct a brief survey assessing decision-making, quality of shared decision-making and telehealth visit (if completed). Patients will receive an additional \$10 upon final survey completion. 								
Outcomes Primary Analysis	Primary Outcome: Completion of LCS counseling, defined by completion of a telemedicine visit, in-person counseling visit (CPT G0296), or documentation of counseling in EHR provider notes. Secondary Outcome: Completion of LDCT scan for LCS Exploratory Outcomes: Decisional conflict and screening preferences Quality of shared decision making and telehealth visit Referral to smoking cessation program Intention-to-treat (ITT) analyses using logistic regression to assess								
	the overall effect of the intervention on completion of LCS counseling.								
Secondary Analyses	 Baseline survey and clinical data will be used to explore potential predictors (demographics, belief and cognitive biases, and other factors) on screening intention and LCS uptake. We will fit multivariable regression models with intervention, moderator, and interaction terms to assess effect modification based on significance of the interaction term. 								
Study Oversight	 Trial oversight will be conducted by the University of Pennsylvania Institutional Review Board. Safety will be monitored on an ongoing basis by the co-PIs and study team. 								

Table of Contents

Principa	al Investigators:	1
Funding	g Agency:	1
Protoco	ol Summary	2
1.	Background and Rationale	6
2.	Objectives	6
2.1.	Specific Aims	6

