5.6. Baseline Survey

Following enrollment, all patients will be asked to complete a brief baseline survey (See Appendix D) accessible through REDCap, assessing demographics, lung cancer screening attitudes and beliefs, decisional conflict and satisfaction, smoking beliefs, and screening intention using measures previously applied in other studies (16-19).

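### The primary logistic regression names no covariates, although screening intention is asked of every enrolled patient before the arm-specific offer and randomization is stratified by batch: a free efficiency gain, not an error

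*Combined protocol and SAP*

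**What the plan says.** **Primary model.** Section 7.3 specifies "Intention-to-treat (ITT) analyses using logistic regression to assess the overall effect of the intervention on completion of LCS counseling among those who enroll". The Protocol Summary says the same in substance. Neither place lists model terms, and neither calls the analysis unadjusted.

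**Baseline data.** Section 5.6 asks all enrolled patients for a survey "assessing demographics, lung cancer screening attitudes and beliefs, decisional conflict and satisfaction, smoking beliefs, and screening intention". In the Protocol Summary (Interventions), the arm-specific step comes afterwards: "Following survey completion: a) Patients in the usual care arm will be provided with contact information for the Penn LCS Program", with the referral offer to the intervention arm at the same point. The Secondary Analysis part of Section 7.3 uses survey data in predictor and moderator models that it labels exploratory; there, screening intention is itself an outcome alongside LDCT uptake.

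**Stratification.** Section 4.2 allocates patients "1:1 stratified by study batch". Batch is not mentioned in Section 7.3.

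**Power.** Section 7.2: "With a sample size of 600 patients across the two arms", 80% power and "Two-sided α =0.05", the trial can "detect a minimum difference of 5.9- 11.4% in the primary outcome (LCS counseling) between the study arms", "depending on completion rate (10-90%) of in controls".

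**Related rules.** Section 5.5 puts patients in the intention-to-treat set at confirmed eligibility and enrollment, not at survey completion. Section 6.4 lets them skip any question. The Protocol Summary and Section 3.3 randomize after the baseline survey, Section 4.2 at survey invitation, and Section 5.7 after consent.

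**The concern.** Completing counseling requires the patient to accept an offer or to contact a program or provider, so stated intention is a plausible predictor of the primary outcome. Aim 2 rests on the idea that such beliefs and characteristics shape screening behavior. In a randomized comparison, pre-specified adjustment for a prognostic baseline value raises power and protects against chance imbalance between arms. Nothing in the design balances intention, because batch is the only stratification factor.

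Two things are at stake. One is efficiency: the trial pays for the survey but does not say that it will use it in the primary comparison. The other is pre-specification: since no covariate list is given, either an adjusted or an unadjusted model would fit the text, and the choice could be made after the data are seen.

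**Working it through.** **Step 1. Reproduce the plan's figure.** Inputs from Section 7.2: n = 300 per arm (600/2), two-sided α = 0.05, power 80%, control rate 10–90%. For a pooled two-proportion test without continuity correction, with d = p₂ − p₁, q = 1 − p and p̄ the mean of the two rates,

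power = Φ{ [d − 1.96·√(2p̄(1−p̄)/n)] / √((p₁q₁ + p₂q₂)/n) }.

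- 90% vs 95.9%: (0.059 − 1.96 × 0.02090)/0.02076 = 0.869, power 80.7%.
- 45% vs 56.4%: (0.114 − 1.96 × 0.04082)/0.04056 = 0.838, power 79.9%.
- Solved for 80% power and an increase in the intervention arm, the detectable difference is 5.85 points at a 90% control rate (the minimum), 7.9 at 10%, and 11.41 near 45–46% (the maximum).

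The stated 5.9–11.4 is reproduced, with no covariate in the calculation. Continuity correction would give 6.1–11.8 and a one-sided test about 5.3–10.1, so neither is what was used.

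**Step 2. Add one baseline score.** The documents give no prognostic strength for intention, so it is assumed and varied. The model is logit P(Y=1) = a + δ·arm + b·X, with X standard normal. The marginal arm rates are held fixed, δ is tested by Wald, and its standard error comes from the Fisher information: power = Φ(δ/SE − 1.96).

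Example, 50% vs 61.34%:
- Without X: 0.4616/0.1655 = 2.789, less 1.96 = 0.829, power 79.7%.
- With X at b = 1.0 (AUC 0.74): 0.5574/0.1827 = 3.051, less 1.96 = 1.091, power 86.2%.

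| Control vs intervention | No adjustment | AUC 0.58 (b = 0.3) | AUC 0.63–0.64 (b = 0.5) | AUC 0.70–0.71 (b = 0.8) | AUC 0.74–0.75 (b = 1.0) |
|---|---|---|---|---|---|
| 10% vs 17.87% | 78.5% | 78.9% (+0.4) | 79.7% (+1.2) | 81.4% (+2.9) | 82.8% (+4.3) |
| 50% vs 61.34% | 79.7% | 80.5% (+0.8) | 81.7% (+2.1) | 84.3% (+4.7) | 86.2% (+6.6) |
| 90% vs 95.94% | 78.7% | 79.0% (+0.2) | 79.4% (+0.7) | 80.5% (+1.8) | 81.6% (+2.9) |

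The unadjusted column falls slightly below 80% because the Wald test on the log odds differs a little from the test in Step 1. With b = 0, adjusted and unadjusted power are equal.

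**Step 3. Rule-of-thumb check.** If baseline values explain a share R² of outcome variance, power ≈ Φ{(1.96 + 0.84)/√(1 − R²) − 1.96}, and the detectable difference shrinks by √(1 − R²).

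- R² = 0.05: power 82%; 11.4 × 0.975 = 11.1 points.
- R² = 0.10: power 84%; 11.4 × 0.949 = 10.8 points.
- R² = 0.20: power 88%; 11.4 × 0.894 = 10.2 points.

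At R² = 0.10 the gain equals 600/0.90 − 600 ≈ 67 more patients. At the planned yield of 600 enrolled from 6,000 invited (Section 3.4), that is about 670 more invitations.

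**Step 4. Effect measure.** The adjusted odds ratio is a different quantity from the crude one. In the example above (AUC 0.74), the marginal odds ratio is 1.59 and the conditional one 1.75. The target therefore has to be named.

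**The case against.** The strongest reply is that nothing here is wrong. The power statement holds without adjustment, the documents call the trial a pilot, and they never call this comparison confirmatory. That stands, and it makes this an improvement and not a correction.

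Three stronger readings are tempting, and the documents do not support them.

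- A reader might infer that the model is fixed as arm only and that the baseline data are deliberately ignored. The text is silent on covariates; it does not rule them out.
- A reader might infer that power is certainly being lost, and by a lot. That needs a strong intention–counseling link, for which no figure is given. Simulated power can reach 91% at 40% vs 51.4%, but only if a 5-level intention score explains 26% of outcome variance. Depending on the score distribution, control completion would then have to rise from about 2–11% at the lowest level to about 64–84% at the highest. The survey asks about intention to be screened while the outcome is counseling, which may also attract undecided patients, so the link could be weak.
- A reader might infer that baseline decisional conflict is used nowhere. The exploratory predictor models draw on the baseline survey and on unnamed other factors, so this cannot be shown.

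A practical objection also stands. A complete-case adjusted model would drop patients who skip items or never finish the survey, against Section 5.5, and could cancel the gain. If Section 4.2 governs, survey completion and skipping also happen after randomization. The arm-specific offer still follows the survey, so bias is unlikely, but the sequence should be stated once and consistently.

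**Conclusion.** The point holds as an efficiency and pre-specification gap. Section 7.3 names no covariates, although a plausible predictor is requested from every enrolled patient before the arm-specific offer and batch is a stratification factor. The sample size and the stated 80% power are sound as they are.

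The gain is about 0 to 7 points of power for a baseline score with AUC up to 0.75: under 1 point at AUC 0.58, and about 3 to 7 points at 0.74–0.75. With no link there is essentially no loss. The direction of the gain is well founded for any prognostic covariate; its size is an assumption, and these figures treat the score as complete and normally distributed.

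**What to change.** Add to Section 7.3 text such as:

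> The primary model includes arm, batch, baseline screening intention (recorded before any arm-specific content), age and sex (age and sex taken from the medical record where available). Patients with missing baseline values, including enrolled patients who do not complete the survey, are kept by a missing category so that every ITT patient is analysed. The arm effect is reported as a standardized (marginal) risk difference with 95% CI, with the unadjusted result as a sensitivity analysis.

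Reconcile the Protocol Summary and Sections 3.3, 4.2 and 5.7 on when randomization occurs relative to the baseline survey. If follow-up decisional conflict is compared between arms, adjust for its baseline value.

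The cost is a few sentences and trivial programming, with no new patients or survey items. The one drawback is that the adjusted odds ratio will not equal the crude one, which reporting the standardized risk difference avoids.
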